CADETTE (Cardiac displacement from third trimester to early childhood)

Fetal heart muscle function in growth retardation.

Significance for the condition of the fetus and for the cardiac function of the newborn and older child

Background

Obstetric ultrasound is an important tool for assessing the fetus during a pregnancy, regarding gestational age, growth and possible malformations. Traditionally, in the routine ultrasound examination, a general assessment is made that the cardiac anatomy is normal. Certain information about the condition of the fetus and placental function is obtained by analyzing flows, for example, in the umbilical cord. An unfavorable intrauterine environment, disturbances in blood flow or substrate supply etc. can result in growth retardation. During a pregnancy with such a complication, repeated considerations are made of the risk of preterm birth versus continued or progressive growth retardation.

New methods for evaluation and treatment of ultrasound data provide improved opportunities to analyze the cardiac muscle function of the fetus.

Our hypothesis is that growth retardation also affects the heart muscle and its function, and that with sensitive methodology, the effect on heart function can be evaluated as an indicator of the general condition of the fetus. Our hypothesis is also that such cardiac function determination can contribute to decision-making when choosing the time of delivery. We also plan to study whether an effect on cardiac function can be demonstrated in newborns and older children who have been stunted intrauterine.

We also want to set cardiac function parameters in growth-retarded and normal fetuses in relation to other data about the fetus/child.

Material and method

This study is a prospective case-control study in which fetuses from normal pregnancies will be compared with fetuses that have intrauterine growth retardation. Parents will be asked in connection with control examinations at the Women's Clinic, where they have been referred due to suspicion of fetal growth retardation. A group of fetuses judged to be growth retarded by specialist ultrasound examination is compared with a control group. The control group is asked among the patients who come for a routine ultrasound in pregnancy weeks 18-20.

Examinations will be carried out in the third trimester and after delivery. During the ultrasound examinations, standardized, moving ultrasound sequences of the heart are saved. Analysis is done offline with Siemens measurement technology (velocity vector imaging, VVI, Siemens medical solutions). With this technique, the chamber wall velocity (velocity), displacement and thickening (strain and strain rate) can be quantified

During the evaluation, the walls of the heart are marked and the software can then produce movement speed and movement in different directions. The fetuses that are part of the control group are examined on 2 occasions, about 4 weeks apart. This takes place during weeks 28-36. For the fetuses that are assessed as growth retarded, image collection is done during the regular ultrasound checks when the pregnancy is followed.

The data we collect about the mother are diseases of the mother and possible treatment. Mother's age, smoking, BMI, possible abnormalities in pregnancy, number of pregnancies and which pregnancy in order. Method of delivery and possible abnormalities during pregnancy such as hypertension, preeclampsia, steroid treatment before birth.

Other data that we plan to collect from the fetus is the flow profile in the umbilical artery, ductus venosus and arteria cerebri media in the fetus. Abdominal circumference, estimated weight. After delivery, check in the journal entries, the child's height, weight, head circumference, gestational age at birth, the acid base of the umbilical vein and the umbilical tree, Apgar score, number of days in hospital for care after delivery, possible complications.

After delivery, we plan to examine the child with ultrasound of the heart at days 1-3, and months 4-6 and at 7 years of age.

[figure not shown]
Sampling of umbilical cord blood and blood samples at age 7 where growth factors and cardiac markers are analyzed.

We plan to examine between 20-30 fetuses with growth retardation and 40-60 fetuses in the control group.

Inclusion of research subjects: Growth retardation during routine ultrasound control of pregnancy, verified during specialist control. Pregnancy length is determined based on the Crown Rump Length taken during the first trimester. Growth retardation is defined by a deviation more than 22% from the normal curve at a given gestational length or a growth rate that deviates more than 10% compared to the previous measurement in relation to expected weight.

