Powercalculation

Artikel 1

Left peak anular velocity during early systole (Left PVS cm/s),

Left peak anular velocity during atrial contraction (Left PVA cm/s)

Right peak anular velocity during atrial contraction (Right PVA cm/s)

Right peak anular velocity during early diastole (Right PVE cm/s)

	Mean Control	Mean Studygroup	SD	2 sided P value 0,05	Power	Sample size	
Left PVS	6,9 (1,2)	5,6 (0,6)	2,0	0,05	0,80	38	
Left PVA	8,5 (1,4)	6,2 (0,7)	2,2	0,05	0,80	15	
Right PVA	10,8 (1,5)	9,1 (1,2)	2,8	0,05	0,80	43	
Right PVE	8,5 (1,3)	6,2 (0,7)	2,5	0,05	0,80	19	

In article 2, which is an overview article on the method, a normal variation of the above-mentioned measurements is specified, a normal variation of approx.

Article 3

In article 3, they have followed Peak systolic tissue velocity (cm/s) in the left and right ventricles

	Mean Control	Mean study group	SD	2 sided P value 0,05	Power	Sample size	If changed to + 20 % in SD
Left ventricle	3,30 (3,05-3,55)	2,41 (1,96-2,86)	0,7	0,05	0,80	10	(SD=1,2) 29
Right ventricle	4,16 (3,88-4,44)	3,98 (3,43-4,53)	1,0	0,05	0,80	485	(SD=1,6) 1241

[name] [name] kliniken Universitetssjukhuset, Linköping

[name] Medicine Doktor Överläkare Kvinnokliniken Universitetssjukhuset, Linköping

[name] [name] kliniken Universitetssjukhuset, Linköping

[name] [name] Linköping

[name] Barnläkare Överläkare Barn och ungdomskliniken Motala/Linköping

[name], verksamhetschef för Barn och ungdomskliniken Motala/Linköping

[name], verksamhetschef för Fysiologiska kliniken, US, Linköping

[name], verksamhetschef för Kvinnokliniken, US, Linköping

Contact

[name],

Barnläkare, doktorand

Barn- och ungdomsmedicinska kliniken

Linköping/Motala

Universitetssjukhuset

[name]

[contact]

epost [contact]

[name]

Medicine Doktor Överläkare

Kvinnokliniken

Universitetssjukhuset

[name]

[contact]

E-post [contact],

[name]
Professor, överläkare
Barn- och ungdomsmedicinska kliniken
Linköping/Motala
Universitetssjukhuset
[name]
[contact]
epost [contact]

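### The power appendix is not reconciled with the planned 20-30 cases and 40-60 controls: its sample sizes are per group at 1:1, and several rows fall short of 0.80 in the planned design

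*Protocol*

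**What the plan says.** Under Material and method, the protocol plans: "We plan to examine between 20-30 fetuses with growth retardation and 40-60 fetuses in the control group". It does not say which calculation these numbers come from.

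Expected results hypothesises a 10% reduction in displacement and velocity in growth-retarded fetuses and refers to an appendix for the power calculation. That appendix (Powercalculation) has one table for article 1 and one for article 3. Both carry the column head "2 sided P value 0,05", a power of 0,80 in every row, and a sample-size column that does not say whether it means per group or in total.

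Two rows show the range. In the article 1 table, the most demanding row reads "Right PVA 10,8 (1,5) 9,1 (1,2) 2,8 0,05 0,80 43"; the other three rows there ask for 38 (left PVS), 15 (left PVA) and 19 (right PVE). In the article 3 table, one row reads "Right ventricle 4,16 (3,88-4,44) 3,98 (3,43-4,53) 1,0 0,05 0,80 485", and its raised-SD figure is 1241 at SD 1,6. The other row of that table, for the left ventricle, asks for 10, or 29 once the SD is raised to 1,2.

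No row is named as the one on which the study is sized.

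**The concern.** Read as totals, 38 and 43 look comfortably covered by the 60 to 90 fetuses planned. Read as numbers per group, they are not covered by 20 to 30 cases unless the larger control group makes up the difference. The appendix is the only sizing basis in the document, so a reader has to be able to tell which measures the planned study can address. If that stays unclear, a null result for right-heart velocity, or for left systolic velocity at the lower end of recruitment, could be given more weight than it can bear.

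**Working it through.** **Inputs.** Means, SD column, alpha and power come from the Powercalculation tables. Group sizes come from Material and method. The 10% effect comes from Expected results. Assumptions: one measurement per fetus, a common SD as in the SD column, and no dropout (none is stated, and zero favours the plan).

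**Step 1: reproduce the printed sample sizes.** Equal groups, two-sided 0.05, power 0.80:

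n per group = 2 × (1.96 + 0.8416)² × (SD/difference)² = 15.70 × (SD/difference)²

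| Row | Difference | SD | Computed n per group | Printed |
|---|---|---|---|---|
| Left PVS | 1.3 | 2.0 | 37.2 | 38 |
| Left PVA | 2.3 | 2.2 | 14.4 | 15 |
| Right PVA | 1.7 | 2.8 | 42.6 | 43 |
| Right PVE | 2.3 | 2.5 | 18.6 | 19 |
| Left ventricle | 0.89 | 0.7 | 9.7 | 10 |
| Left ventricle, raised SD | 0.89 | 1.2 | 28.5 | 29 |
| Right ventricle | 0.18 | 1.0 | 484.5 | 485 |
| Right ventricle, raised SD | 0.18 | 1.6 | 1240.3 | 1241 |

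Rounded up, all eight match. Other readings do not. A one-sided test gives 30, 12, 34, 15, 8, 23, 382 and 977. Taken as totals, the printed numbers would give power of only about 0.42 to 0.51.

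**Step 2: put the planned design on the same scale.** The equal-group equivalent of unequal groups is 2 × n1 × n2 / (n1 + n2):

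- 20/40: 2 × 20 × 40 / 60 = 26.7 per group
- 30/60: 2 × 30 × 60 / 90 = 40.0 per group

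Against this, left PVS (38) is missed at the low end and met at the top. Right PVA (43) and right ventricle (485) are missed throughout. Left ventricle at SD 1.2 (29) is missed at the low end.

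**Step 3: achieved power.** Noncentrality = difference / (SD × √(1/n1 + 1/n2)). For left PVS at 20/40 this is 1.3 / (2.0 × 0.2739) = 2.37. The normal approximation gives Φ(2.37 − 1.96) = 0.66, and the noncentral t gives 0.65. By noncentral t for all rows, with the article difference and with 10% of the control mean:

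| Row | Article difference, % of control mean | Power 20/40 | Power 30/60 | Power at 10%, 20/40 | Power at 10%, 30/60 |
|---|---|---|---|---|---|
| Left PVS | 18.8 | 0.65 | 0.82 | 0.24 | 0.33 |
| Left PVA | 27.1 | 0.96 | >0.99 | 0.28 | 0.40 |
| Right PVA | 15.7 | 0.59 | 0.77 | 0.28 | 0.40 |
| Right PVE | 27.1 | 0.91 | 0.98 | 0.23 | 0.32 |
| Left ventricle, SD 0.7 | 27.0 | >0.99 | >0.99 | 0.40 | 0.55 |
| Left ventricle, SD 1.2 | 27.0 | 0.76 | 0.91 | 0.17 | 0.23 |
| Right ventricle, SD 1.0 | 4.3 | 0.10 | 0.125 | 0.32 | 0.45 |
| Right ventricle, SD 1.6 | 4.3 | 0.07 | 0.08 | 0.15 | 0.21 |

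**Step 4: what 0.80 needs at 1:2.** Cases = 1.5 × (1.96 + 0.8416)² × (SD/difference)², with twice as many controls:

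- Left PVS: 27.9, so 28 cases and 56 controls (29 cases by t-test)
- Right PVA: 31.9, so 32 and 64 (33 cases by t-test)
- Right ventricle at SD 1.0: 363.4, so 364 and 727 (365 cases by t-test)

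**The case against.** **No promise is broken.** The 0,80 is an input beside alpha, and the sample size is the output. The rows are scenarios drawn from two articles, none is called primary, and the plan nowhere says that its numbers give 80% power for any of them. This stands. A reader might infer that the protocol guarantees 0.80 for all six measures and then fails to deliver it, but the text does not support that. What remains is that the only power calculation asks for sizes that the design does not provide for some rows, and nothing connects the two.

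**The right-ventricle shortfall is in plain sight.** The printed 485 exceeds the planned maximum of 90 fetuses whether read per group or in total, and its 4.3% effect lies below the hypothesised 10%. This also stands. The row is not concealed; the protocol simply draws no conclusion from it.

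**The other misses are partial.** At 30/60 left PVS passes and right PVA is 0.77. True, but left PVS is still at 0.745 at 25/50, and right PVA starts at 0.59.

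**The SD column may be too large.** The article 1 means carry smaller, unlabelled bracketed values. If those are SDs, power for left PVS and right PVA exceeds 0.99 even at 20/40. The document does not say what they are. The printed sample sizes rest on the SD column, so the gap holds on the table's own terms, but the source of that column needs stating.

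**Repeated examinations could help.** Controls are examined twice and cases at their regular checks. If two measurements per fetus were averaged with an assumed correlation of 0.5 to 0.8, right PVA at 30/60 would have power of about 0.87 to 0.81, and left PVS about 0.91 to 0.86. At 20/40 both stay below 0.80. The appendix does not claim this gain.

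**Conclusion.** The concern holds as a failure to reconcile the power appendix with the planned numbers. The appendix figures are per group at 1:1, without saying so, and the planned design is equivalent to 26.7 to 40 per group. On the table's own means and SD column, with one measurement per fetus and a t-test, right PVA and right ventricle do not reach 0.80 at any planned size. Left PVS reaches it only from about 28-29 cases with twice as many controls. Left ventricle at SD 1,2 falls short at 20/40.

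A reader might also conclude that the three remaining rows are safely powered. That is so only for differences of about 27% taken from the articles. At the protocol's own 10% hypothesis, with the same SDs, they have power 0.23 to 0.55, and no row in the appendix reaches 0.80.

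This should be fixed, but it does not invalidate the study. The document sets no rule that a null result will be taken as absence of effect, and the finding gives no reason in itself to change enrolment.

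**What to change.** In the power appendix:

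1. Label the sample-size column as per group, 1:1.
2. Add achieved power at 20/40 and 30/60 for every row, including the raised-SD rows, for both the article difference and the hypothesised 10% reduction. Showing only the article difference would present three measures as powered when they are not powered for the stated hypothesis.
3. State that right PVA and right ventricle do not reach 0.80 at any planned size, and treat both as exploratory. State that left PVS reaches 0.80 only from about 28-29 cases with twice as many controls.
4. State where the SD column comes from and what the bracketed values beside the article 1 means are. If the SDs change, recompute the added columns.

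If the analysis will use the repeated examinations to gain precision, say so and give the correlation assumed.

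The cost is a few sentences and some extra columns, with no change in enrolment. The downside is a less favourable stated power.

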Powercalculation

Artikel 1

Left peak anular velocity during early systole (Left PVS cm/s),

Left peak anular velocity during atrial contraction (Left PVA cm/s)

Right peak anular velocity during atrial contraction (Right PVA cm/s)

Right peak anular velocity during early diastole (Right PVE cm/s)

	Mean Control	Mean Studygroup	SD	2 sided P value 0,05	Power	Sample size	
Left PVS	6,9 (1,2)	5,6 (0,6)	2,0	0,05	0,80	38	
Left PVA	8,5 (1,4)	6,2 (0,7)	2,2	0,05	0,80	15	
Right PVA	10,8 (1,5)	9,1 (1,2)	2,8	0,05	0,80	43	
Right PVE	8,5 (1,3)	6,2 (0,7)	2,5	0,05	0,80	19	

In article 2, which is an overview article on the method, a normal variation of the above-mentioned measurements is specified, a normal variation of approx.

Article 3

In article 3, they have followed Peak systolic tissue velocity (cm/s) in the left and right ventricles

	Mean Control	Mean study group	SD	2 sided P value 0,05	Power	Sample size	If changed to + 20 % in SD
Left ventricle	3,30 (3,05-3,55)	2,41 (1,96-2,86)	0,7	0,05	0,80	10	(SD=1,2) 29
Right ventricle	4,16 (3,88-4,44)	3,98 (3,43-4,53)	1,0	0,05	0,80	485	(SD=1,6) 1241

[name] [name] kliniken Universitetssjukhuset, Linköping

[name] Medicine Doktor Överläkare Kvinnokliniken Universitetssjukhuset, Linköping

[name] [name] kliniken Universitetssjukhuset, Linköping

[name] [name] Linköping

[name] Barnläkare Överläkare Barn och ungdomskliniken Motala/Linköping

[name], verksamhetschef för Barn och ungdomskliniken Motala/Linköping

[name], verksamhetschef för Fysiologiska kliniken, US, Linköping

[name], verksamhetschef för Kvinnokliniken, US, Linköping

Contact

[name],

Barnläkare, doktorand

Barn- och ungdomsmedicinska kliniken

Linköping/Motala

Universitetssjukhuset

[name]

[contact]

epost [contact]

[name]

Medicine Doktor Överläkare

Kvinnokliniken

Universitetssjukhuset

[name]

[contact]

E-post [contact],

[name]
Professor, överläkare
Barn- och ungdomsmedicinska kliniken
Linköping/Motala
Universitetssjukhuset
[name]
[contact]
epost [contact]
